(13 Jan 2024 Protocol number: 1)

4. Funding:

Self-funding

5. Roles and responsibilities:

Supervisors and principal investigator:

Main supervisor :

- [name] [name].

Professor of Oral Medicine and Periodontology- Cairo University, Faculty of Dentistry, Cairo University.

Role:

- Initiation and idea of the clinical trial.
- Randomization and allocation of cases.
- Supervision of the clinical procedures.
- Auditing for writing and final report result.

Co-Supervisor:

[name] .

Lecturer of Oral Medicine , Periodontology and Oral diagnosis , Faculty of Dentistry, Cairo University.

Role :

- Randomization and allocation of cases
- Supervise the surgical procedures.
- Collection, management, interpretation, and analysis of data.
- Auditing for writing and final report result

Co-Supervisor:

Ass. [name] [name]

Associate Professor of Periodontics, Faculty of Dentistry, Fayoum University, MSA University.

Role:

- Initiation and idea of the clinical trial.
- Randomization and allocation of cases
- Supervise the surgical procedures.
- Collection, management, interpretation, and analysis of data.
- Auditing for writing and final report result

Principal Investigator:

- [name] .

Master's degree candidate, Department of Oral Medicine and Periodontology, Faculty of Dentistry, Cairo University.

Role:

- Follow up recording.
- Writing the thesis.
- Protocol writing.
- Collection, management, interpretation, and analysis of data.
- Enrolment of study population.
- Performing surgical procedures (treatment).
- Data collection.
- Submitting the report for publication.

Trial responsibility:

Department of Oral Medicine and Periodontology, Faculty of Dentistry, Cairo University.

Committees:

- Research plan committee.
- Periodontology department council.
- Evidence based dentistry committee.
- Faculty Council.
- Ethics committee

II. Introduction:

6. Background and rationale:

Research question:

In patients with non-restorable dentition in the maxillary esthetic zone indicated for immediate implant placement, will buccal plate augmentation using sticky bone results in superior pink esthetic score compared to sticky bone used to fill the jumping gap?

Statement of the problem:

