- Blood will be centrifuged at a speed of 700 rpm for 3 minutes. An orange- colored fluid will be formed as the upper layer in the test tubes i.e., I- PRF. Approximately 1 ml of I-PRF will be collected in a syringe.
- Solid-PRF + Liquid-PRF mixed DBBM: Solid-PRF membranes will be mixed thoroughly with 0.25 g of DBBM particles. Then 1 mL Liquid PRF from the buffy coat layers will be added drop by drop to the DBBM.
- Following polymerization by 15-20 minutes, sticky bone will be ready to be grafted.
- The sticky bone graft will be condensed and adapted into the jumping gap as well as over the implants.
- the healing abutment will be screwed into the implant body .

Intervention group:

- A thin periosteal elevator will be used to reflect the soft tissue buccal to the bony buccal plate on the mid-facial aspect of the socket in a full-thickness manner, following a corono-apical direction, thereby creating a ‘surgical pouch’.
- The dissection will be advanced beyond the mucogingival line to approximately two-thirds the depth of the socket, and the ‘pouch’ will be expanded in the mesio-distal direction to stretch the soft tissues away from the underlying bony plate.
- Sticky bone will be inserted into the pouch by a mean of a small periosteal elevator. Additional graft material will be added and compressed until adequate filling of the pouch is achieved without overstressing the soft tissues.
- the healing abutment will be screwed into the implant body .

Postoperative Care:

Administration of:

- 1 gm Amoxicillin 500 mg (Misr Co. for Pharmaceutical Industries, Egypt) three times a day for seven days, or doxycycline 100 mg (Nile Co. for Pharmaceuticals and Chemical Industries, Egypt) twice a day if they are penicillin sensitive. [68]
- Ibuprofen 400 mg (Brufen, Kahira Pharmaceuticals, Egypt) will be provided for severe pain. [68]
- 0.12% Chlorhexidine mouthwash twice daily for two weeks. [68]

Patient self-care instructions:

- Avoid any hard brushing and trauma to the surgical site for two weeks.
- Participants will be instructed to avoid causing any damage to the operated site and to avoid consuming hot meals or vigorous rinsing.

Postoperative Radiographs:

- A standardized periapical parallel radiograph will be taken on the same day after implant placement to assess crestal bone level then after 3 and 6 months. CBCT scan will be scheduled for six months postoperative.

12. Outcomes:

PICOT:

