P: Patients with non-restorable tooth in the maxillary esthetic zone including anterior and premolars indicated for immediate implant placement.

I: Buccal plate augmentation using sticky bone

C: Sticky bone used as a jumping gap filling material

O: Pink Esthetic score (PES)

T: 6 months

Outcome	Outcome name	Measuring device	Measuring unit
Primary outcome	Pink esthetic score	using the PES scoring system for dental implants.[71]	Numerical
Secondary outcome	Crestal bone level	CBCT machine . [69]	Millimeter
	Thickness of labial plate of bone	CBCT machine . [29]	Millimeter
	Soft tissue profile /contour	Scanning of diagnostic casts by optical scanner.[69]	Millimeter
	Patient satisfaction	VAS based questionnaire.[70]	Binary

13. Participant timeline

	Preoperative assessment	Immediately after implant placement	3 months post operative	6 months post operative
Pink esthetic score			X	X
Crestal bone level	X			X
Thickness of labial plate of bone	X			X
Soft tissue profile /contour	X		X	X
Patient satisfaction		X	X	X

Clinical evaluation:**1) pink esthetic score :[71]**

This pink esthetic score (PES) evaluates the esthetic outcome of soft tissue around implant-supported single crowns in the anterior zone by awarding seven points for the mesial and distal papilla, soft-tissue level, soft-tissue contour, soft-tissue color, soft-tissue texture, and alveolar process deficiency. With the exception of papilla formation, the evaluation is performed visually by comparing reference teeth (i.e., with the contralateral tooth in the incisor zone and adjacent tooth in the premolar zone). For the mesial and distal papilla, the categories are complete, incomplete, and absent. For each criterion it is possible to award a score between two points (for a very good outcome) and no points (for a poor outcome). The maximum score that can be achieved is 14 points indicating an outcome that reflects complete conformity between the soft tissue of the tooth being assessed and that of the reference tooth.

Specific measurement time point: 3 and 6 months postoperatively.

2) crestal bone level : [69]

Cone beam computed tomography (CBCT) machine with superimposition technique.

Specific measurement time point: baseline and 6 months postoperatively.

3) Thickness of labial plate of bone:[29]

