Using CBCT machine . Using the axial view, one reference line will be drawn from the apex of the implant to its platform (long axis); another line, perpendicular to the one at the long axis, will be drawn at the apex of the implant. Parallel to this, two lines will be drawn, one at 1 mm from the implant collar (R1) and another 5 mm apical to it (R2) measuring the thickness of the bone (at the buccal plate) to the nearest 0.1 mm.

Specific measurement time point: baseline and 6 months postoperatively.

4) Soft tissue profile /contour:[69]

Scanning of diagnostic casts by optical scanner.

Specific measurement time point: baseline , 3 and 6 months postoperatively.

14. Sample size:

Pink Esthetic Score (PES) was chosen as the primary outcome variable and effect size was estimated to be 1.5 based on a previous study by Abdelraheem et al (2022). Power calculation was performed at $\alpha=0.05$ and at $\beta=0.20$, equal to 80% of power. Under this assumption, at least 8 patients were needed for each group with a total number of 16 patients. This number was increased to 20 patients (10 patients in each group) to compensate for any possible dropouts.

15. Recruitment:

- Patients will be selected from the outpatient clinic of the Oral Medicine and Periodontology department, Faculty of Dentistry-Cairo University.
- Screening of patients will continue until the target sample is achieved. (Consecutive sampling)

B) Assignment of interventions

16. Allocation:

All patients who provide an informed consent for participation as well as fulfill the inclusion criteria will be included in the study.

16a. Randomization:

Patients will be randomly assigned to either test or control groups using computer generated randomization (www.randomizer.org) which will be performed by the main supervisor.

16b. Allocation concealment mechanism:

Allocation concealment will be done by creating opaque sealed envelopes. The envelope will be chosen by the patient and will only be opened after completion of extraction.

16c. Implementation

- The supervisor will generate the randomization sequence. The principal investigator will enroll the participants.

17. Masking/blinding:

- Blinding of the operator is not applicable.
- Participants, Outcome assessor (primary and secondary outcomes) & biostatistician will be blinded.

C) Data collection, management, and analysis:

18. Data collection methods

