- The phone numbers and address of the patients included in the study will be recorded or extracted from the patients' files.
- The baseline outcomes data as well those at follow-up periods will be assessed by co-supervisor.

Plans to promote participant retention and complete follow- up:

- Telephone numbers of all patients included in the study will be recorded as a part of the written consent.
- All patients will receive a phone call at the time of the pre-determined follow up.

19. Data management:

- All data will be entered and saved electronically.
- Patients' files are to be stored in numerical order and stored in a secured file. Data will be encrypted using a password.
- All data will be maintained after completion of the study.

20. Statistical methods:

Data will be analyzed using IBM SPSS advanced statistics (Statistical Package for Social Sciences), version 21 (SPSS Inc. Chicago, IL). Numerical data will be described as mean and standard deviation or median and range or interquartile range, as appropriate. Categorical data will be described as numbers and percentages. The data will be explored for normality using Kolmogrov-Smirnov test and Shapiro-Wilk test. Comparisons between two groups and over time will be done by 2-way analysis of variance for repeated measures.

If the time factor is not considerable, comparisons between the two groups for normally distributed numeric variables will be done using the Student's t-test while for non- normally distributed numeric variables will be done by Mann-Whitney test.

A p-value less than or equal to 0.05 will be considered statistically significant. All tests will be two-tailed.

D) Data monitoring:

21. Monitoring

No formal data monitoring committee will be needed since it is a study with known minimal risks.

22. Harms

Any temporary or permanent adverse effect will be recorded and documented.

No Harms are expected.

23. Audit

No formal auditing committee is available.

IV. Ethics and dissemination

24. Research ethics approval

This protocol and the template informed consent form will be reviewed by the Ethics Committee of Scientific Research -Faculty of Oral and Dental Medicine, Cairo University.

25. Protocol amendments

Any modifications to the protocol which may have an impact on the conduct of the study, potential benefit of the patient, or may affect patient safety, including changes of study objectives, study design, sample sizes, study

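### The outcome assessor is declared blinded, yet is an unnamed co-supervisor, and both co-supervisors are listed to supervise the surgery at which the arm becomes visible

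*Protocol*

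**What the plan says.** - **Blinding (Section 17).** The operator is not blinded. For the others the Protocol states: "Participants, Outcome assessor (primary and secondary outcomes) & biostatistician will be blinded".
- **Who assesses (Section 18).** "The baseline outcomes data as well those at follow-up periods will be assessed by co-supervisor". The singular is used and no one is identified, although Section 5 lists two co-supervisors.
- **Roles (Section 5).** Both co-supervisors carry the duty "Supervise the surgical procedures". Both are also listed for randomization and allocation and for handling and analysing the data. The main supervisor separately has "Supervision of the clinical procedures".
- **When the arm is revealed (Section 16b).** "The envelope will be chosen by the patient and will only be opened after completion of extraction".
- **What is then done (Section 11).** Control: "The sticky bone graft will be condensed and adapted into the jumping gap as well as over the implants". Intervention: "Sticky bone will be inserted into the pouch by a mean of a small periosteal elevator".
- **How the primary outcome is scored (clinical evaluation of PES, under Section 13).** "With the exception of papilla formation, the evaluation is performed visually by comparing reference teeth". There are seven criteria, each scored 0 to 2, with a maximum of 14. PES is read at 3 and 6 months only.

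**The concern.** The section on blinding and the sections on who does what do not fit together. If the assessing co-supervisor carries out the surgical duty listed for both co-supervisors, that person knows the arm before scoring the patient at 3 and 6 months.

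PES is the outcome most exposed. Five of its seven criteria are visual comparisons with a reference tooth, and the two papilla criteria are graded in three categories. A rater who knows the arm can lean towards one technique without intending to. Any lean that differs between arms enters the estimated treatment effect, and the planned tests cannot tell it apart from a real difference. Because PES has no baseline reading, every PES score is taken after the arm has been revealed.

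A report that repeated Section 17 would also claim a protection that the listed roles undercut.

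**Working it through.** **Step 1. Set the sections side by side.**

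| Question | Section | Answer in the Protocol |
|---|---|---|
| Is the assessor blinded? | 17 | Yes, for primary and secondary outcomes |
| Who is the assessor? | 18 | A co-supervisor, not identified |
| Who supervises surgery? | 5 | The main supervisor and both co-supervisors |
| When is the arm revealed? | 16b | After extraction, within the surgical session |
| Can an onlooker tell the arms apart? | 11 | Yes: graft in the gap around the implant, or graft in a dissected buccal pouch |
| Is either co-supervisor kept out of surgery or allocation? | none | No such statement |

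It makes no difference which co-supervisor is meant in Section 18, since both hold the surgical duty.

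**Step 2. Look for another safeguard.** Section 27 puts coded IDs on data forms, but gives confidentiality as the purpose. Section 29 strips identifying participant information from data passed to the team. Neither masks someone who saw the operation and later examines the same patient. No masked photographs and no independent rater are described.

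**Step 3. Allocation duties.** Section 16a gives randomization to the main supervisor, and Section 16c gives sequence generation to the supervisor. Section 5 also lists both co-supervisors for randomization and allocation. This is a second route by which the assessor could learn the arm, and the sections do not agree on it.

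**Step 4. Which outcomes are exposed.** PES is exposed at both visits. Crestal bone level, labial plate thickness and soft tissue contour are read in millimetres from CBCT or cast scans and are less exposed. Patient satisfaction is a patient questionnaire. Preoperative readings precede the opening of the envelope and cannot be affected.

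**Step 5. Illustrate the size.** Inputs from the Protocol: 10 patients per arm (Section 14) and two-sided testing at 0.05 (Section 20). Assumed, because the documents do not give them: the SD of PES (1, 1.5 or 2) and an average scoring shift in one arm (0.1, 0.2 or 0.5 points). A shift of 0.5 corresponds to one criterion moved by one point in 5 of 10 patients (5 × 1 / 10), and a shift of 0.1 to the same in 1 of 10. The true effect is set to zero.

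Noncentrality of the t-test: shift / (SD × √(2/n)), with 2n − 2 degrees of freedom. For a shift of 0.5, SD 1 and n = 10: 0.5 / (1 × 0.447) = 1.118 on 18 degrees of freedom, which gives a rejection rate of 18.5%.

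| Shift (points) | SD 1 | SD 1.5 | SD 2 |
|---|---|---|---|
| 0.1 | 5.5% | 5.2% | 5.1% |
| 0.2 | 7.1% | 5.9% | 5.5% |
| 0.5 | 18.5% | 10.9% | 8.3% |

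A simulation of 200,000 trials agreed closely (for shift 0.5: 18.5%, 10.9%, 8.4%). With 8 per arm, the number before the dropout allowance, a shift of 0.5 gives 15.4%, 9.5% and 7.5%.

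Section 20 also plans a repeated-measures analysis of variance. Its group effect is equivalent to a t-test on the mean of the two visits, so the SD is multiplied by √((1 + ρ)/2), where ρ is the between-visit correlation. With the same shift at both visits and ρ assumed between 0.5 and 0.9, the range over SD 1 to 2 is 5.1 to 5.7% for a shift of 0.1, 5.5 to 7.8% for 0.2, and 8.4 to 23.1% for 0.5.

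**The case against.** Section 17 makes a specific commitment, whereas Section 5 is a generic list with nearly the same bullets for several people. Nothing states that the assessing co-supervisor attends each operation. With three supervisors available, one could stay out of surgery and assess blind. **This stands as far as it goes:** the text does not prove that blinding will be broken. But it gives the same surgical duty to both candidates and exempts neither, so it does not secure the blinding.

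The allocation bullet in Section 5 might mean only supporting tasks, such as preparing envelopes. That reading is possible, but such tasks would also have to be kept from a blinded assessor.

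The error rates rest on an assumed bias and an assumed SD. **This also stands.** They show what a bias of a given size would do, not that one will occur. Only a shift that differs between arms matters, and the cap of 14 limits upward movement for scores near the maximum, which the calculation ignores.

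Finally, the principal investigator operates, so knows the arm, and is listed in Section 5 for follow-up recording and data collection. **This is a fair addition.** Naming one sole assessor settles who scores the outcomes, and those bullets should be worded to match. Section 29 also gives the supervisors access to the data sets. The Protocol does not say whether these carry the allocation.

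**Conclusion.** The point holds and should be corrected before any outcome is scored, because an assessor who has seen the arm cannot be blinded again. As written, the assessor blinding in Section 17 conflicts with the roles in Sections 5 and 18 and is not secured. Actual unblinding is not shown.

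The weight of the point rests on the primary outcome being a largely visual score with an unblinded operator, not on the assumed error rates. Under those assumptions the inflation is negligible for a bias of 0.1 points and becomes material only near half a point (8.3 to 18.5% for the t-test with 10 per arm). The concern is essentially PES at 3 and 6 months; the CBCT and cast-scan measures are less exposed. The sample size is not affected.

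**What to change.** 1. In Section 18, name one of the two co-supervisors, by role, as sole assessor of PES, crestal bone level, labial plate thickness and soft tissue contour.
2. In Section 5, remove that person's surgical-supervision and allocation duties. The main supervisor, who already oversees the clinical procedures, and the other co-supervisor cover surgery.
3. Make Sections 5, 16, 17 and 18 agree on who randomizes, who supervises surgery and who assesses. Word the principal investigator's follow-up-recording and data-collection bullets so that they do not include scoring these outcomes.
4. State that the assessor has no access to the allocation, including through the data sets covered by Section 29, until scoring is complete.
5. If neither co-supervisor can be released from surgery, withdraw the assessor-blinding claim from Section 17. That makes the document truthful but leaves PES open to assessor bias, so it is the second choice.

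**Cost:** protocol wording and a duty roster, with no new staff, visit or procedure. The price is that one co-supervisor stays out of surgery, and the documents do not say whether one can.

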- Systemic health conditions that contraindicate or affect healing of implant surgery (Diabetes Mellitus, Leukemia)
- Pregnant and nursing females.
- Smokers.

11. Interventions

Preoperative phase:

All patients will undergo pre-operative clinical examination: Patient's data will be collected; name, gender and age, medical and dental histories will be taken. Also, all patients will undergo standardized periapical radiograph to detect any pathosis and a pre-operative Cone beam computed tomography (CBCT) scans will be taken to evaluate the tooth root configuration and to confirm the presence of intact buccal wall, Vital structures related to the tooth, Vertical and horizontal dimensions of the alveolar bone and Bone density.[68]

Patient preparation for surgical procedure:

After extra oral disinfection of the surgical site, the patients will be asked to rinse their mouths with Chlorohexidine HCL 1.25% mouthwash (Orovex mouthwash, Macro group, Egypt) immediately preoperatively. Local infiltration anesthesia [Articaine 4% 1:100,000 epinephrine] (Artinibsa 40mg/0.1 mg/ML - epinephrine 1:100000, Spain) will be used for all procedures.[68]

Control group:

- The surgical procedure will be performed in sterile surgical field. Under local anesthesia, sharp dissection of the supracrestal fibers will be done with no.15 c scalpel blade. With the purpose of preserving the buccal and palatal bone walls, periomes, elevators and maxillary root forceps will be used to facilitate atraumatic extraction.
- The socket will be well irrigated with saline and debrided with a bone curette. An intact buccal bone plate should be found after extraction of the tooth.
- Bony sockets will be prepared through sequential drilling for the placement of the implant.
- Achieving primary stability after implant placement will be followed by placement of cover screw.
- Venous blood will be withdrawn under aseptic conditions by veni puncture of the antecubital vein and transferred into sterile tubes which will be devoid of anticoagulants. I- PRF preparation will be done using the protocol developed by Mourão et al. [67]
- Plastic PET tubes to create Liquid-PRF, while glass tubes will be used to obtain Solid-PRF.
- Blood will be centrifuged at a speed of 3000 rpm for 10 minutes to obtain autologous PRF plug.

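### Secondary outcomes with a baseline: section 20 never uses baseline as a covariate; ANCOVA is a cheap, modest gain for contour, and for the two bone outcomes only once a usable baseline exists

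*Protocol*

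**What the plan says.** Protocol section 20 sets two routes for numeric outcomes. The main one is "Comparisons between two groups and over time will be done by 2-way analysis of variance for repeated measures". The other begins "If the time factor is not considerable, comparisons between the two groups for normally distributed numeric variables" and names Student's t-test, with the Mann-Whitney test for variables that are not normal. No covariate is named in the protocol.

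Three secondary outcomes have a scheduled baseline (sections 12 and 13):

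- **Soft tissue contour**, in millimetres: "Specific measurement time point: baseline , 3 and 6 months postoperatively". The timeline table agrees and places the baseline before surgery. The method is given only as "Scanning of diagnostic casts by optical scanner.[69"; the quantity read from each scan is not defined.
- **Crestal bone level** and **labial plate thickness**, in millimetres: baseline and 6 months, by CBCT.

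PES is scored only at 3 and 6 months, so it has no baseline. The sample size in section 14 rests on PES. Under section 16b the allocation envelope is opened only after extraction, so a preoperative measurement precedes allocation.

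**The concern.** With 8 to 10 patients per arm, precision on the secondary outcomes is low, and a pre-allocation baseline is one of the few free ways to improve it. With a baseline and one follow-up, the group-by-time term of the repeated-measures ANOVA is the same as a comparison of change scores. That is inefficient when baseline and follow-up are weakly correlated. A t-test on the 6-month value alone is inefficient when they are strongly correlated. The correlation is not known in advance, and whether time matters, which is how section 20 chooses the route, does not tell the investigator which route is more precise. ANCOVA stays close to the better of the two over the whole range. At stake is the width of the intervals for secondary outcomes, not the validity of any test.

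**Working it through.** **Inputs.** From the protocol: two-sided 0.05 (section 20); 8 patients per arm needed and 10 recruited (section 14). The stated 8 per arm reproduces: a t-test with effect size 1.5 has power 0.797. That calculation concerns PES and is not in question.

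Assumed, because the documents give no figure: normal data with equal SDs; a 6-month difference of 1.2 SD; correlation ρ between baseline and 6 months from 0 to 0.9; no time trend common to both arms; and the section 20 condition on time read as a non-significant time effect.

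**Variances.** For baseline plus one follow-up, n per arm, relative to the t-test on the 6-month value:

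- t-test: 1
- change score (group-by-time): 2(1 − ρ)
- ANCOVA: (1 − ρ²)k, with k = 1 + 1/(2n − 4). This is 1 + 1/16 = 1.0625 at n = 10 and 1 + 1/12 = 1.083 at n = 8.

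ANCOVA equals the t-test where ρ = √(1 − 1/k): 0.24 at n = 10 and 0.28 at n = 8. At ρ = 0 it has 6% or 8% more variance. ANCOVA equals the change score where ρ = 2/k − 1: 0.88 at n = 10 and 0.85 at n = 8. At ρ = 0.9 it has 1% or 3% more variance.

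**Power, 10 per arm, 1.2 SD** (exact noncentral t for the t-test and the interaction, simulation for the rest):

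| ρ | Interaction | 6-month t-test | Two-step plan | ANCOVA | ANCOVA minus two-step plan |
|---|---|---|---|---|---|
| 0 | 44% | 72% | 60% | 69% | 9 |
| 0.3 | 57% | 72% | 64–65% | 73% | 8–9 |
| 0.5 | 72% | 72% | 73% | 81% | 8 |
| 0.7 | 91% | 72% | 89% | 93% | 4 |
| 0.9 | 100% | 72% | 100% | 100% | 0 |

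At 8 per arm and the same ρ values, the interaction has 35/47/61/82/100%, the t-test 61%, and ANCOVA 57/61/69/85/100%. Type I error is near 0.05 for all of these.

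**Contour with three visits**, 10 per arm, ρ 0.3/0.5/0.7. If the effect is equal at 3 and 6 months, the interaction F test has 61/76/94% against 73/81/93% for the 6-month ANCOVA, so there is no gain at 0.7. If the effect at 3 months is half as large, the figures are 48/63/86% against 73/81/93%.

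**Non-normal data.** On normal data, a rank-based (Quade) ANCOVA has 67/70/77/88% at ρ 0/0.3/0.5/0.7 against 67% for Mann-Whitney (10 per arm). Part of that gain is test size, because the exact Mann-Whitney test rejects only 4.2–4.4% under the null. On log-normal data, plain ANCOVA has 57/63/77% against 53/64/79% for the interaction at ρ 0.3/0.5/0.7, so there is little or no gain.

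**Is there a baseline to adjust for?**

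- *Contour:* the timing is consistent and precedes allocation. A covariate exists if each scan yields its own millimetre value. It does not exist if the value is a surface difference from the baseline cast.
- *Labial plate thickness:* section 13 draws the measurement lines (R1, R2) from the implant's apex, platform and collar. The only CBCT before 6 months is preoperative (section 11: "pre-operative Cone beam computed tomography (CBCT) scans will be taken to evaluate the tooth root configuration"; afterwards "CBCT scan will be scheduled for six months postoperative"), when there is no implant.
- *Crestal bone level:* section 11 describes a periapical radiograph "taken on the same day after implant placement to assess crestal bone level then after 3 and 6 months". Section 13 describes CBCT with superimposition, and its table marks the baseline as preoperative. These passages must be reconciled. If superimposition gives only a change, there is no separate baseline value.

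**The case against.** The strongest reply is that this is a preference between valid tests on secondary outcomes, and that covariates are often left to the SAP. The first half stands: no test here is biased and the primary result does not move. The second half does not dispose of the point, because section 20 itself names the tests and the remark improves a stated method.

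Four stronger readings are tempting and are not supported:

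- *The fallback ignores baseline.* Section 20 does not say which value enters the t-test or Mann-Whitney test. A test on change fits the wording and would use baseline.
- *The gain is about 25 points.* That is ANCOVA against the interaction alone at ρ = 0 (69% against 44%). The plan is conditional, and under the reading above the gain is 0 to 9 points. A strong time trend in both arms would send more trials to the interaction and raise the gain at low ρ.
- *The ANOVA dilutes the effect.* Averaging baseline with follow-up would halve the 6-month effect only if the group main effect were the treatment test. The text does not say so, and the group-by-time term is valid.
- *All three outcomes can be adjusted at once.* Two have no usable baseline as written, and contour depends on an undefined measured value.

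**Conclusion.** The point holds as a cheap improvement to secondary analyses. For outcomes with a baseline, both section 20 routes are valid but generally less efficient than ANCOVA. The gain over the two-step plan is about 0 to 9 points of power at 10 per arm. It rests on an assumed 1.2 SD difference, no common time trend, and a time condition read as a significance test. Against a t-test on the 6-month value alone, ANCOVA loses up to about 3 points (10 per arm) or 4 points (8 per arm) when ρ is below about 0.25–0.3. Near ρ = 0.9 it has no advantage over the change comparison. The gain is therefore likely but not certain. PES, the primary conclusion and the sample size are unaffected.

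**What to change.** Add to section 20:

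- **Contour.** Provided one millimetre value is recorded from each cast scan (preoperative, 3 and 6 months), compare the 6-month value between arms by ANCOVA with the preoperative value as covariate. The alternative is a model of both follow-up visits with arm, visit, arm-by-visit, baseline and baseline-by-visit terms; with complete data it gives the same 6-month estimate. Report the adjusted difference with its 95% CI. If the recorded value is itself a difference from the baseline cast, keep the between-arm comparison of change.
- **Non-normal data.** Use a rank-based ANCOVA, for the p-value only, since it gives no adjusted difference or interval.
- **Repeated-measures ANOVA including baseline.** Keep it to describe change over time.
- **Crestal bone level, and labial plate thickness at R1 and R2 separately.** Apply the same rule only after sections 11 and 13 are reconciled so that a pre-allocation baseline in the same metric exists. Otherwise keep the comparison of change.

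**Cost:** a few sentences, one degree of freedom, and up to 6–8% more variance than the t-test if ρ is near zero. Contour needs no new visit or scan, but the quantity read from each cast must be defined and recorded. Reconciling the two bone baselines is separate work.
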